8.7 Premature termination of the study

A premature termination of the study is not expected to happen as there are only limited safety risks. Adverse events are not expected, since maltodextrin and dietary prebiotics have been proved to be safe. In addition, subjects will be checked on the remission status, so any complaints will be reported in time. In case of unexpected adverse events that harm the subjects, the study will be stopped immediately. In case of premature termination, we still intend to analyse and publish the results of the part of the study that has been completed.

9. SAFETY REPORTING

9.1 Temporary halt for reasons of subject safety

In accordance to section 10, subsection 4, of the WMO, the sponsor will suspend the study if there is sufficient ground that continuation of the study will jeopardise the subject health or safety. The sponsor will notify the accredited METC without undue delay of a temporary halt including the reason for such an action. The study will be suspended pending a further positive decision by the accredited METC. The investigator will take care that all subjects are kept informed.

9.2 AEs, SAEs and SUSARs

9.2.1 Adverse events (AEs)

Adverse events are defined as any undesirable experience occurring to a subject during the study, whether or not considered related to [the investigational product/trial procedure/ the experimental intervention]. All adverse events reported spontaneously by the subject or observed by the investigator or his staff will be recorded.

9.2.2 Serious adverse events (SAEs)

A serious adverse event is any untoward medical occurrence or effect that

- results in death;
- is life-threatening (at the time of the event);
- requires hospitalisation or prolongation of existing inpatients' hospitalisation;
- results in persistent or significant disability or incapacity;
- is a congenital anomaly or birth defect; or
- any other important medical event that did not result in any of the outcomes listed above due to medical or surgical intervention but could have been based upon appropriate judgement by the investigator.

An elective hospital admission will not be considered as a serious adverse event.

The investigator will report all SAEs to the sponsor without undue delay after obtaining knowledge of the events. The sponsor will report the SAEs through the web portal *ToetsingOnline* to the accredited METC that approved the protocol, within 7 days of first knowledge for SAEs that result in death or are life threatening followed by

a period of maximum of 8 days to complete the initial preliminary report. All other SAEs will be reported within a period of maximum 15 days after the sponsor has first knowledge of the serious adverse events. In case of AEs or SAEs, the study may be prematurely terminated if the health or safety of the subject is at risk.

9.2.3 Suspected unexpected serious adverse reactions (SUSARs)

Not applicable.

9.3 Annual safety report

Not applicable.

9.4 Follow-up of adverse events

All AEs will be followed until they have abated, or until a stable situation has been reached. Depending on the event, follow up may require additional tests or medical procedures as indicated, and/or referral to the general physician or a medical specialist. SAEs need to be reported till the end of study within the Netherlands, as defined in the protocol.

9.5 [Data Safety Monitoring Board (DSMB) / Safety Committee]

Not applicable.

10. STATISTICAL ANALYSIS

Statistical analyses will be done using the statistical program embedded within R. The threshold for significance will be set at $p<0.05$, with a FDR correction for 16S rRNA gene sequence data. In general, the continuous data will be presented as mean \pm standard deviation or mean and interquartile range when skewed, and categorical data as counts and percentages. Normality will be checked by visual inspection and QQ plots, followed by the Shapiro Wilk test for testing if data show a normal distribution.

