4.4 Sample size calculation

The primary objective of the trial is to validate the prediction that a higher response (lower mean P-SCCAI score) is induced at T= 8 weeks by the prebiotics intervention in mild UC patients with low Bacteroidetes levels (predicted responders), but not in those with high Bacteroidetes levels (predicted non-responders) in their gut. Mild UC is defined as a P-SCCAI score of 3 to 5. According to an extensive study regarding UC disease activity conducted in the Netherlands, mild UC patients have a P-SCCAI score of 3.5 ± 0.5 (Mean \pm standard deviation (SD)), and patients in remission score at 1.0 ± 0.33 (Mean \pm SD)[34, 35].

In a series of germinated barley foodstuff (GBF) intervention studies, 10 mild to moderately active UC patients received 30 grams of GBF (equals to 10 grams fiber) daily for 4 weeks [4], and researchers found a significant decrease in clinical activity index scores. In a later study, another group of 11 mildly to moderately active UC patients consuming 20-30 grams of GBF (equals to 6.66-10 g fiber) daily for 4 weeks showed similar results, with decreases in clinical activity index scores [28].

Based on two-sided statistical testing for unpaired continuous data, an $\alpha=0.05$ (chance on type-I error) and $\beta=0.10$ (chance on type-II error), and assuming a 20% difference of mean P-SCCAI score between predicted responders with prebiotics and predicted non-responders with prebiotics, it was calculated that at least 11 subjects per group are needed for the primary outcome P-SCCAI ($\mu_1=3.5$; $SD_1=0.5$; $\mu_2=2.8$). According to previous trials on prebiotics on IBD patients, a 20% of drop-out rate is commonly seen. Given that the intervention duration is 8 weeks long, followed by a 1 year follow-up, higher dropout rate (30%) is expected. To compensate for a 30% drop-out rate, 15 subjects per group are needed.

To reach inclusion of 30 predicted responders and 30 predicted non-responders, we made an estimate how many subjects we need to screen based on the earlier obtained microbial composition of stool samples from UC patients in the Ede area. Around 50% of these subjects were categorized as low Bacteroidetes subjects (predicted responders) and while 17% of them as high Bacteroidetes subjects (predicted non-responders). To include these responders we will need to screen 177 mild UC patients.

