10.2 Secondary study parameter(s)

Response over time

To assess the response over time, data of mean P-SCCAI score within each arm at T = 0, 4, 8, 12 and 60 weeks will be obtained. Comparisons will be made between groups (as done for T = 8 for the primary study parameter) as well as within subjects over time. With P-SCCAI score ≤ 2 being regarded as clinical remission, and a decrease in the P-SCCAI score by more than two points from baseline being regarded as clinical response, we will determine whether subjects have reached clinical remission and/or showed a clinical response over time.

To assess the response within each subject (clinical remission and/or clinical response) over time, data of sum P-SCCAI score within each subject at T = 0, 4, 8, 12 and 60 weeks will be obtained. For comparative analyses between baseline and intervention, the parametric paired sample T-test or the non-parametrical Kruskal-Wallis or Mann-Whitney

U test will be used, depending on the distribution of the samples. Differences between treatments before and after supplement intake will also be analysed by linear mixed models for repeated measures, using “treatment” [prebiotics/placebo], “responding” [responders/non-responders], “time point” [0, 4, 8, 12 and 60 weeks] and “treatment x responding x time point” as fixed effects and subject as random effect. Clinically relevant variables such as BMI, age, sex, and medication use will be taken into account.

Mucosal inflammation

Fecal calprotectin data will be analysed in the same manner as described above (Response over time).

GI complaints:

Data from GSRS will be computed into scores, and the score of each item will be pooled together as the sum score, and the score of each item within each domain will be pooled as well. All data will be analysed in the same manner as described above (Response over time). Differences over time within and between groups will be tested with mixed model analysis. Variables such as timepoint, group, age, sex will be taken into account.

Stool consistency and frequency

Average bowel movement per day and dynamic change on stool consistency will be calculated and collected. All data will be analysed in the same manner as described above (Response over time)..

Gut microbiota and SCFAs

Fecal SCFAs data will be analysed in the same manner as described above (Response over time)

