16S rRNA gene sequencing provides sequence read counts data. It will be normalized to microbial relative abundance, and microbiota diversity indices (Shannon, Simpson, and inverse Simpson) are calculated at amplicon sequence variant (ASV) level, as implemented in the Picante [66] and Phyloseq [67] packages in R, respectively. Wilcoxon test will be applied to determine whether diversity as well as the relative abundance of specific bacterial taxa, were significantly different between groups since the data was non-parametric. For microbiota analysis, *p*-values will be corrected for multiple comparisons using the Benjamini–Hochberg procedure. To correct for a false discovery rate (FDR), a FDR adjusted *p*-values will be computed, a so-called *q*-value [68]. A corrected *q*-value of less than 0.2 was considered significant. Paired tests will be used to

compare the effects of prebiotics. Pairwise weighted UniFrac [69] and unweighted UniFrac [70] distance-based principle coordinate analysis (PCoA) will be used to visualize microbial community variation at the ASV level. Permutational multivariate analysis of variance (PERMANOVA) will be used to test for significant differences between groups, as implemented in the Vegan package [71].

Health-related quality of life

Data from SIBDQ will be computed into scores, and the score of each item will be pooled together as the sum score, and the score of each item within each domain will be pooled as well. All data will be analysed in the same manner as described above (Response over time).

Medication use

Type, Dose, frequency and duration of each medication use will be collected. All data will be analysed in the same manner as described above (Response over time).

Safety parameters

Incidence rate of each adverse event is recorded and calculated. All data will be analysed in the same manner as described above (Response over time).

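### Section 10 calls every non-16S secondary test significant at uncorrected p<0.05: about 82 randomised contrasts, about 4 expected false positives if the prebiotic does nothing

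*Protocol*

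**What the plan says.** Protocol section 10 opens with a general rule: a significance threshold of p<0.05, "with a FDR correction for 16S rRNA gene sequence data". Section 10.2 describes the Benjamini-Hochberg procedure, at a q-value below 0.2, for the microbiota analysis only.

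Section 10.1 defines three pairwise comparisons for the primary endpoint: predicted responders against predicted non-responders, both on prebiotics; prebiotics against placebo in predicted responders; and prebiotics against placebo in predicted non-responders. Section 10.2 carries them over to P-SCCAI at the other visits: "Comparisons will be made between groups (as done for T = 8 for the primary study parameter) as well as within subjects over time". For GSRS and SIBDQ both the sum score and the domain scores are analysed ("the score of each item within each domain will be pooled as well"). Calprotectin, stool measures, SCFAs, GSRS, SIBDQ, medication use and safety all refer back to the P-SCCAI analysis, typically with "All data will be analysed in the same manner as described above (Response over time".

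Section 10.2 also plans paired tests against baseline and a repeated-measures mixed model with treatment, stratum, time point and their three-way interaction. The document does not say which of these analyses takes precedence, or that any of them is exploratory.

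**The concern.** This is a rule written into the protocol, not a detail left open. Taken as written, any non-16S secondary comparison with p<0.05 is significant, however many are run.

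Two features make that matter here. First, the primary objective in section 2 says the prebiotic raises butyrate production and thereby improves symptoms, but the only main endpoint in section 8.1.1 is P-SCCAI at week 8. The butyrate part is therefore tested only through the SCFA data, which sit inside this uncorrected family. Second, the arms are small: 15 patients each, planned so that 11 remain after drop-out. A few isolated p-values below 0.05 could be read as support for the butyrate or symptom hypothesis even if the primary comparison is negative.

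**Working it through.** **Figures in the plan.** The protocol gives no number of secondary tests and no expected number of false positives, so there is nothing to reproduce on this point. Its one related calculation is the arm size in section 4.4 ("it was calculated that at least 11 subjects per group are needed for the primary outcome P-SCCAI"). With a difference of 3.5 − 2.8 = 0.7, SD 0.5, two-sided alpha 0.05 and 90% power, 2 × (1.960 + 1.282)² × 0.5² / 0.7² = 10.7, so 11 per group. That agrees. It is powered for one comparison and allows nothing for the secondary tests.

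**Counting the secondary cells.** A cell is one score at one post-baseline visit. Visits and domains come from sections 8.1.2 and 10.2.

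| Outcome | Scores | Post-baseline weeks | Cells |
|---|---|---|---|
| P-SCCAI, week 8 excluded as primary | 1 | 4, 12, 60 | 3 |
| Fecal calprotectin | 1 | 8, 12, 60 | 3 |
| GSRS sum and five domains | 6 | 4, 8 | 12 |
| Stool frequency and consistency | 2 | 4, 8 | 4 |
| SCFAs (three assumed) | 3 | 8, 12, 60 | 9 |
| SIBDQ sum and four domains | 5 | 4, 8 | 10 |
| Total | | | 41 |

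The number of SCFAs is an assumption. The protocol names only butyrate.

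**Randomised contrasts** (prebiotics against placebo in each stratum):
- Tests: 41 × 2 = 82.
- Expected false positives if the prebiotic does nothing: 82 × 0.05 = 4.1, whatever the correlation between tests.
- One SCFA: 35 cells, 70 tests, 3.5 expected. Four SCFAs: 44 cells, 88 tests, 4.4 expected.
- Narrowest count, sum scores only and one SCFA: 17 cells, 34 tests, 1.7 expected. This ignores the domain scores that section 10.2 says will be analysed.
- Wider count, three SCFAs: adding clinical remission and clinical response at weeks 4, 8, 12 and 60 gives 41 + 8 = 49 cells, 98 tests, 4.9 expected. Adding medication use (4 cells) and adverse events (2 cells) gives 55 cells, 110 tests, 5.5 expected.

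**Spread around the expectation.** If the 82 tests were independent, the chance of at least one false positive would be 1 − 0.95^82 = 98.5%. They are not independent: sum scores contain their domains, and visits repeat within patients. In a simulation with no effect, 41 measures per patient, a common correlation of 0.5 and 11 or 15 patients per arm, the mean stayed near 4 (3.95 and 4.21). The chance of at least one fell to about 84%, and the median was 2 to 3.

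**Non-randomised contrast** (predicted responders against predicted non-responders, both on prebiotics):
- Tests: 41 × 1 = 41.
- Expected false positives: 41 × 0.05 = 2.05, but only if the strata do not differ for reasons other than treatment.
- With an assumed stratum difference of 0.5 SD and an inert prebiotic, the same simulation gave about 8 of these 41 tests below 0.05 at 11 per arm, and between 10 and 11 at 15 per arm.

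**Before-after tests.** These cannot be given an expected number of false positives under an inert prebiotic. Section 4.2 selects patients at P-SCCAI 3 to 5 with a recent exacerbation, so an arm's mean may move from baseline through natural course or regression to the mean.

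**The case against.** The strongest reply is that the protocol names a single main endpoint and labels the rest secondary, that multiplicity rules for secondary outcomes are often set in a statistical analysis plan, and that many statisticians accept unadjusted secondary p-values when they are read as exploratory. The planned mixed models also give a more economical summary than visit-by-visit tests. Part of this stands: correcting all secondary endpoints is not obligatory, and the absence of a correction would not by itself be an error. But section 10 states a rule, calls the results significant under it, and gives no exploratory label. The mixed models are run in addition to the pairwise tests, so they do not reduce the count.

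Some stronger readings are tempting and are not supported:

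- A reader might multiply all three contrasts, 41 × 3 = 123 tests, and conclude that 123 × 0.05 = 6.15 false positives follow if the prebiotic does nothing. The arithmetic is right but the condition is wrong. The strata are defined by Bacteroidetes level, so an inert prebiotic does not make the responder against non-responder contrast null.
- A reader might count four arms × 42 cells (week 8 P-SCCAI now included) = 168 before-after tests and expect 8.4 false positives. That requires no change over time in any arm, which the selection of patients does not support. It also counts weeks 12 and 60, although the paired tests are described for baseline against intervention.
- A reader might say that the plan already holds a 5% false discovery rate procedure and chose not to apply it here. The plan's level for microbiota is q<0.2, and silence about the other outcomes shows no intent.

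**Conclusion.** The point holds in limited form. Under the stated rule, about 82 randomised secondary comparisons would be judged at uncorrected p<0.05, with about 4 expected to be significant by chance if the prebiotic has no effect (3.5 to 4.4 for one to four SCFAs). The figure rests on post-baseline visits only, sum and domain scores as section 10.2 specifies, and one test per score, visit and contrast. It is an expectation: with correlated outcomes some trials would show none and others many.

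The non-randomised contrast adds about 41 tests. Its roughly 2 further false positives hold only if the strata are otherwise alike. If they are not, it can produce more significant results that say nothing about the prebiotic. The before-after tests add results of the same uninformative kind, which cannot be counted in advance. The three primary comparisons are outside this point.

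**What to change.** In section 10, replace the single-threshold sentence with a rule for the non-16S secondary outcomes:

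- Comparisons with baseline within an arm are descriptive and carry no significance claim.
- Between-arm secondary results are exploratory and are reported as estimates with 95% confidence intervals.
- Where significance is claimed, it rests on Benjamini-Hochberg-adjusted values over the randomised prebiotic-placebo contrasts, at a false discovery rate written into the text. The 16S analysis uses q<0.2, so any different level has to be stated.
- The comparison of predicted responders with predicted non-responders is kept out of that family and described as non-randomised.

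The cost is a few sentences and one extra adjustment step in R, with no new data or patients. The downside is that fewer secondary results can be called significant. If a separate statistical analysis plan exists, it should carry the same rule, so that the two documents do not disagree.

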10.1 Primary study parameter(s)

Response (mean P-SCCAI score) between arms at T = 8 weeks

To assess the response, data of mean P-SCCAI score within each arm at T = 8 weeks (after the intervention) will be obtained.

Firstly, the mean P-SCCAI score between the predicted responders with prebiotics and predicted non-responders with prebiotics will be compared by using a Student T-test if normally distributed, otherwise a Mann-Whitney U test when skewed.

Secondly, the mean P-SCCAI score between prebiotics and placebo groups within predicted responders or predicted non-responders will be compared by using a Student T-test if normally distributed, otherwise a Mann-Whitney U test when skewed.

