8. METHODS

8.1 Study parameters/endpoints

8.1.1 Main study parameter/endpoint

Response (mean P-SCCAI score) between arms at T = 8 weeks:

At T = 8 weeks (the end of the intervention), the P-SCCAI score will be collected via the P-SCCAI questionnaire. As main endpoint, the mean P-SCCAI score for each arm will be determined and compared to each other to determine the difference in response at T = 8 weeks.

P-SCCAI is derived from the original SCCAI questionnaire by translating into patients' comprehensible language, and has been validated to give substantial agreement with the original SCCAI [54]. P-SCCAI refers to disease symptoms during the previous week. It contains 13 items clustered into six domains: bowel frequency (during the day), bowel frequency (during the night), urgency of defecation, blood in stool, general well-being, and a number of defined extracolonic features of UC (i.e. arthritis, erythema nodosum, pyoderma angrenosum, uveitis).

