8.1.2 Secondary study parameters/endpoints

Response over time

In addition to week 8, subjects need to fill out the P-SCCAI questionnaire at T = 0, 4, 12, and 60 weeks to determine the response over time. Comparisons will be made between groups as well as within subjects over time. With P-SCCAI score <= 2 being regarded as clinical remission, and a decrease in the P-SCCAI score by more than two points from baseline being regarded as clinical response [30, 31, 55] (see F1). We will also determine whether subjects have reached clinical remission and/or showed a clinical response over time.

Mucosal inflammation

At T= 0, 8, 12, and 60 weeks, a fecal sample will be provided by subjects for calprotectin measurement.

GI complaints: (e.g. abdominal pain, bloating, flatulence)

At T= 0, 4, and 8 weeks, the GI complaints will be assessed by the GSRS questionnaire. The GSRS contains 15 items clustered into five domains (reflux, abdominal pain, indigestion, diarrhea and constipation) addressing different gastrointestinal symptoms [56]. It has a seven-point graded scale where 1 represents the absence of troublesome symptoms and 7 represents very

troublesome symptoms (see F1). The reliability and validity of the GSRS are well-documented, and norm values for a general population are available [57].

Stool consistency and frequency

At T = 0, 4, and 8 weeks, subjects will be asked to keep diaries to record stool frequency (bowel movement per day) and consistency of each stool using Bristol stool form scale (see F1) on a daily basis for 7 days.

Gut microbiota and SCFAs: (e.g. microbiota composition, SCFAs profile)

At T = 0, 8, 12, and 60 weeks, a fecal sample will be provided by subjects for 16S rRNA gene-based microbiota profiling and SCFAs measurement. Subsequent analyses of a variety of microbial ecological characteristics, including microbiota composition, α -diversity (diversity within the sample), β -diversity (diversity between the samples), population dynamics over time, and group differences will also be conducted.

Health-related quality of life

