At baseline, selected participants need to fill out several questionnaires P-SCCAI, FFQ [60], GSRS [61], Bristol stool form scale [62], stool frequency, SIBDQ [58], information of medication use and adverse events will be extracted from patient record and diary. All questionnaires can be found in F1 Questionnaires. The GSRS questionnaire provides baseline GI complaints and tolerance information. P-SCCAI provides disease activity information. FFQ provides information regarding the usual foods consumed and the frequency of consumption. Bristol stool form scale provides stool consistency information. SIBDQ provides information on health-related quality of life.

One stool sample will also be provided. The sample will undergo the same collection and storage procedures as those in the screening period. DNA will be isolated from part of the stool samples and subsequently be used for 16S rRNA gene-based microbiota profiling using NG-Tax [63]. The stool sample will be also used for measurements of fecal calprotectin using enzyme-linked immunosorbent assay (ELISA) methods [64], and SCFAs concentrations using high-performance liquid chromatography (HPLC) [65].

Dietary intervention period (8 weeks)

During the intervention period, the subjects will consume the respective supplement (3 grams/sachet) twice per day. To minimize potential GI complaints that might occur due to intake of the prebiotics/placebo supplement, there will be a gradual increase in dosage that only 1 sachet daily will be consumed in the first week of the intervention period, followed by 2 sachets daily for the remainder of the intervention. The patients will be asked to save all the empty sachets.

At T= 4, and 8 weeks, subjects will also need to complete short questionnaires on response (P-SCCAI, once a week), GI complaints and tolerance (GSRS, once a week), stool frequency and consistency (Bristol stool form scale, a 7-day record at each week), SIBDQ (once a week). Information of medication use and adverse events will be extracted from patient record and diary (once a week).

At the end of the intervention period (T= 8 weeks), the participants will provide a second stool sample for fecal calprotectin measurements, 16S rRNA gene-based microbiota profiling, and SCFAs profile analysis. We will determine response with P-SCCAI score.

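### The primary test in section 10.1 leaves out the T=0 P-SCCAI score, so a baseline gap in the non-randomised arm 1 v arm 3 contrast could pass, partly or fully, into the week-8 result

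*Protocol*

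**What the plan says.** Section 8.1.1 defines the main endpoint at week 8 between arms: "the mean P-SCCAI score for each arm will be determined and compared to each other". Section 10.1 names the data, "data of mean P-SCCAI score within each arm at T = 8 weeks (after the intervention) will be obtained", and then the first comparison: "the mean P-SCCAI score between the predicted responders with prebiotics and predicted non-responders with prebiotics will be compared". The second set of comparisons is prebiotics v placebo within each Bacteroidetes group. All are two-sample tests on the week-8 score, with no baseline value, change score or covariate.

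The baseline score is available. Section 8.1.2 states that "subjects need to fill out the P-SCCAI questionnaire at T = 0, 4, 12, and 60 weeks", and section 8.3 repeats it: "At baseline, selected participants need to fill out several questionnaires P-SCCAI".

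Section 10.2 uses T=0 only for secondary purposes: group comparisons at each time point, paired tests, the definition of clinical response, and a mixed model in which T=0 is one of the outcome time points.

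Sections 3 and 8.3 set the predicted-responder groups by Bacteroidetes share (10% or less v 15% or more). Section 8.2 randomises patients only to prebiotics or placebo. Section 4.4 sizes the trial on arm 1 v arm 3.

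**The concern.** Nothing in the design balances disease activity at T=0 between low- and high-Bacteroidetes patients. If arm 1 starts lower than arm 3, the week-8 test can show a difference that was already there. If arm 1 starts higher, a real difference can be hidden. The protocol calls the endpoint response, and sections 8.1.2 and 10.2 define clinical response as a fall from baseline. The lead test, however, cannot tell patients who improved from patients who began with fewer symptoms. At stake is the comparison on which the primary objective and the sample size rest.

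**Working it through.** **Inputs from the protocol.** Section 4.4: means 3.5 and 2.8 (difference 0.7), SD 0.5, two-sided alpha 0.05, power 90%, 11 per group, 15 after allowing for dropout. Section 4.2: entry P-SCCAI 3 to 5.

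**Assumptions, not in the protocol.** Correlation r between T=0 and week-8 score, 0 to 0.5; T=0 gap between arms 1 and 3 of 0, 0.25 or 0.5 points; normal scores; the same SD at both times.

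**The plan's own figure.** n = 2 x [0.5 x (1.960 + 1.282) / 0.7]^2 = 10.72, so 11 per group, as stated. Power by the exact t distribution at 11 per group is 87.7%.

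**Bias with no true effect.**
- Gap shrinks with regression to the mean: the raw week-8 difference is r x gap. For a gap of 0.5 and r = 0.5 it is 0.25, against a planned difference of 0.7. Adjusting for T=0 leaves about zero.
- Gap persists unchanged: the raw difference is the full gap. Adjustment removes r x gap and leaves (1 - r) x gap. For a gap of 0.5 that is 0.40 at r = 0.2 and 0.25 at r = 0.5.
- r = 0 and the gap does not persist: nothing carries over.

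**Scale check.** The standard error of the raw difference is 0.5 x sqrt(2/11) = 0.213. A carried-over difference of 0.25 is 1.17 standard errors; one of 0.5 is 2.35.

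**Simulated false-positive rates** (60,000 trials per setting, 11 per arm, SD 0.5, r 0.2 to 0.5; ANCOVA is the linear model with T=0 as covariate):

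| Gap at T=0 | Course of gap | Raw t-test | ANCOVA | Change score |
|---|---|---|---|---|
| 0.25 | shrinks | 6-9% | 5% | 9-11% |
| 0.5 | shrinks | 7-20% | 5% | 20-29% |
| 0.25 | persists | 20% | 9-14% | 5% |
| 0.5 | persists | 61% | 20-36% | 5% |

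**Masking.** True difference 0.7, arm 1 worse at T=0 by 0.25, gap shrinking: power is 83% raw v 85% adjusted at r = 0.2, 80% v 87% at r = 0.3, and 73% v 92% at r = 0.5.

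**Cost of adjusting, true difference 0.7.**
- No gap: raw power is about 88%. ANCOVA gives 86%, 87%, 89% and 94% at r = 0, 0.2, 0.3 and 0.5.
- r = 0 with a gap of 0.25: 88% raw v 83-84% adjusted, a loss of about 4 points.
- r = 0 with a gap of 0.5: 88% raw v 77% adjusted, a loss of about 11 points.

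The extra loss arises because group and T=0 score are then correlated. The ANCOVA variance is proportional to 2/n + d^2/Sxx, where d is the observed T=0 gap and Sxx is about 20 x 0.25 = 5. With d = 0.5 this is 0.182 + 0.050, so the standard error rises by about 13%.

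**The case against.** **Size.** The harm depends on two quantities that the protocol does not give, and the largest rates need a gap of a full planning SD. Every patient enters at 3 to 5 points, whichever Bacteroidetes group they join. A check with baseline limited to 3, 4 or 5, rounded week-8 scores, a shrinking gap, slope 0.2 to 0.5 and week-8 residual SD 0.5 to 1.5 (all assumed) gave raw false-positive rates of 5-7% at a gap of 0.25 and 5-14% at 0.5. This stands: the effect is likely smaller than the table shows. It does not remove the point, because the entry band is 2 points wide against a planned difference of 0.7.

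**Adjustment is not free.** This also stands. At r = 0.1 and a gap of 0.5 with arm 1 worse, power is 83% raw v 77% adjusted. Nor is one method right in both scenarios: ANCOVA is unbiased if the gap shrinks to r x gap, the change score if it persists.

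**Section 10.2 already uses T=0.** It extends the group comparisons to every time point ("Comparisons will be made between groups (as done for T = 8 for the primary study parameter") and adds the mixed model, so a gap would be seen. That does not change the result of the primary test. Nor is this a detail left to a SAP, since section 10.1 itself fixes the data, contrasts and tests.

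**Stronger readings that a reader might infer.**
- That the arms do differ at T=0: the protocol has no data on this.
- That the randomised comparisons are invalid: randomisation protects prebiotics v placebo within each group. With whole-point scores and entry at 3 to 5, adjustment changed power there by only about -1 to +4 points.
- That the choice between the t-test and its fallback, "otherwise a Mann-Whitney U test when skewed", is a comparable fault: section 10 names the check ("Normality will be checked by visual inspection and QQ plots, followed by the Shapiro Wilk test") and no inflation of type I error was shown, so it is not raised as a separate point.

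**Conclusion.** The point holds as a moderate one. Section 10.1 leaves a baseline score that is already collected out of the primary test, and the lead contrast has no randomisation to balance that score. The percentages in the table are conditional on the assumed r and gap, 11 completers per arm, SD 0.5 and unrestricted normal scores; they show what could happen and do not estimate what will. In every gap scenario computed with r between 0.2 and 0.5, the adjusted test had a lower or equal false-positive rate than the raw test. When r is near zero and a gap exists, adjustment loses power and gains nothing. A correlation of exactly zero between the same symptom score eight weeks apart is the extreme case, so adjustment is the better default. It would still leave arm 1 v arm 3 an observational comparison, exposed to every other difference between low- and high-Bacteroidetes patients.

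**What to change.** In section 10.1, make each primary comparison a pre-specified linear model of week-8 P-SCCAI on group with T=0 P-SCCAI as covariate, reporting the adjusted mean difference with its 95% confidence interval. For arm 1 v arm 3, add the difference in change from baseline as a named sensitivity analysis. State that, for this contrast, adjustment reduces bias from the measured baseline score, may not remove it, and does not make the contrast randomised. Make the change before unblinding, so that the choice of analysis does not follow from an observed gap.

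The cost is two or three sentences and one degree of freedom per model, with no new visits, data or patients. The price in power is the loss at low r shown in the working; with no gap, power rises from r of about 0.3 upward.
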